## 5.0 SUBSTUDY TREATMENT

There will be no study treatment provided by A5352s. Participants will continue to take their randomized A5350 regimens. See section 5.0 of A5350 for study product requirements.

## 5.1 Prohibited Medications

Use of the following medications during the substudy are prohibited:

- Aspirin, antiplatelet agents, NSAIDs which cannot be held as above for flexible sigmoidoscopy and lactulose/mannitol gut permeability test.
- Medications as specified in the main study, A5350.

### 6.0 CLINICAL AND LABORATORY EVALUATIONS

### 6.1 Schedule of Events

	Screening (Within 45		Week 1 (±4 days)	Post-Entry On Treatment		
Evaluation	days prior to substudy entry)	Entry		Week 24 (at least 14 days prior to Week 26) (±7 days)	Week 26 (±7 days)	
Hematology	Х			Х		
Urine for Gut Permeability Assessment by LMR			x		Х	
Sigmoidoscop y with Colonic Biopsies		×		Х		

# 6.2 Timing of Evaluations

## 6.2.1 Screening and Pre-Treatment Evaluations

# Screening

Screening evaluations to determine eligibility must be completed within 45 days prior to substudy entry unless otherwise specified.

In addition to data being collected on participants who enroll into the substudy, demographic, clinical, and laboratory data on screening failures will be captured in a Screening Failure Results form and entered into the ACTG database.

### Entry

Entry evaluations must be completed at least 24 hours after screening evaluations.

NOTE: At the time of a sigmoidoscopy visit, the participant must avoid drinking alcohol or taking nonsteroidal anti-inflammatory medications, including aspirin or any blood thinners for 7 days prior to the test.

### Week 1

Week 1 evaluations must be completed at least 4 days after entry evaluations unless otherwise specified.

NOTE: At the time of a sugar absorption test visit, the participant must have avoided drinking alcohol for 3 days prior to the test, avoided taking nonsteroidal

anti-inflammatory medications, including aspirin or any blood thinners for 7 days prior to the test, and have abstained from exercise the day before and the morning of the test.

## 6.2.2 Post-Entry Evaluations

## **On-Treatment Evaluations**

All on-treatment evaluations must be scheduled as per section 6.1 with a ±7 day window.

### 6.2.3 Discontinuation Evaluations

Evaluations for Registered Participants Who Do Not Start Study Intervention
All CRFs must be completed and keyed for the period up to and including week
1.

No follow-up evaluations are required for registered participants who do not have the first biopsy.

## Premature Discontinuation Evaluations

Participants who prematurely discontinue the substudy (ie, elect not to have the second biopsy) will be taken off the substudy. No further substudy evaluations are required.

Site personnel should notify the protocol core team via e-mail ([contact]) within 48 hours after a participant indicates his/her intention to prematurely discontinue the substudy.

## 6.3 Instructions for Evaluations

All clinical and laboratory information required by this protocol is to be present in the source documents. Sites must refer to the Source Document Guidelines on the DAIDS Web site for information about what must be included in the source document: http://www.niaid.nih.gov/labsandresources/resources/daidsclinrsrch/documents/sourced-ocappndx.pdf

### 6.3.1 Adverse Events

An adverse event (AE) is any unfavorable and unintended sign (including an abnormal laboratory finding), symptom, or disease having been absent at baseline, or, if present at baseline, appears to worsen AND is temporally associated with medical treatment/study product/device or procedure, REGARDLESS of the attribution (ie, relationship of event to medical treatment/study product/device or procedure).

To grade diagnoses, signs and symptoms, and laboratory results, sites must refer to the DAIDS Table for Grading the Severity of Adult and Pediatric Adverse Events (DAIDS AE Grading Table), Version 2.0, November 2014, which can be

found on the DAIDS RSC Web site: http://rsc.tech-res.com/safetyandpharmacovigilance/.

- 6.3.1.1 SAEs are adverse events that result in one or more of the following outcomes:
  - Results in death
  - Life-threatening
  - Requires inpatient hospitalization or prolongation of existing hospitalization
  - · Results in persistent or significant disability/incapacity
  - · Congenital anomaly/birth defect
  - Other important medical event (may not be immediately lifethreatening or result in death or hospitalization but may jeopardize the patient or may require intervention to prevent one of the events listed above.

NOTE: SAEs should be entered into the AE log and into the DAERS system as indicated.

6.3.1.2 Any adverse event related to the sigmoidoscopy with biopsies or the Lactulose/Mannitol testing must be reported regardless of grade as an AE on the A5350 AE log.

## 6.3.2 Laboratory Evaluations

At screening and week 24, all hematology laboratory values are recorded in the source document only.

Hematology INR and PT/PTT

## 6.3.3 Urine for Gut Permeability Assessment by LMR

Urine will be collected for 5 hours after administration of a standard oral solution containing lactulose and mannitol. Gut permeability assessment will be performed at least 7 days after flexible sigmoidoscopy. Additional details about the lactulose/mannitol test are included in the study MOPS.

## 6.3.4 Sigmoidoscopy with Colonic Biopsies

Colonic biopsies collected by flexible sigmoidoscopy will be obtained per the SOE to assess tissue-specific effects related to immunologic outcomes, inflammation, bacterial translocation, and gut integrity. Immunohistochemistry will be used to assess the total numbers of CD4+ and CD8+ T-cells, neutrophil infiltration, IL-17 expression, and markers of microbial translocation. Additional details about the flexible sigmoidoscopy procedure and colonic biopsy are included in the study MOPS.

Colonic biopsy specimens will be stored for possible future genetic testing.

## 6.3.5 Immunologic Assays on Colonic Biopsy Specimens

Colonic biopsy specimens will be collected per section 6.1 and evaluated for:

- Total numbers of CD4+ and CD8+ T-cells
- Neutrophil infiltration
- IL-7 expression
- Markers of microbial translocation

Colonic biopsy specimens will be processed and stored according to the LPC.

## 7.0 CLINICAL MANAGEMENT ISSUES

# 7.1 Sigmoidoscopy and Colonic Biopsies

On extremely rare occasions, a sigmoidoscopy may cause pain, infection, bleeding, or perforation of the GI tract (occurs about once out of every 1000 procedures and may require hospitalization and surgical management).

Any incidental clinical findings will be followed up at the time of the procedure if possible (eg, removal of incidental polyps or biopsy of abnormal lesions). All abnormal findings will be referred for further appropriate care under the direction of the site gastroenterologist.

### 8.0 CRITERIA FOR DISCONTINUATION

### 8.1 Permanent and Premature Discontinuation

- Procedure-related complication, that in the opinion of the local investigator, prohibits the participant from continuing in the substudy (see section 7.1)
- Discontinuation of ART on A5350
- At the discretion of the IRB, NIAID, Office for Human Research Protections (OHRP), or other government agencies as part of their duties
- Reguest by participant to terminate the substudy
- Clinical reasons believed life-threatening by the physician, even if not addressed in the toxicity section of the protocol

## 9.0 STATISTICAL CONSIDERATIONS

### 9.1 General Design Issues

A5352s is a substudy of A5350 that will evaluate administration of Visbiome Extra Strength therapy compared to placebo on change in rectal lamina propria CD4+ T-cell

numbers among HIV-infected participants ≥18 years of age who have been on stable ART for at least 24 weeks prior to study entry, and have CD4+ T-cell >200 cells/mm3 prior to study entry and plasma HIV RNA <50 copies/mL for 48 weeks prior to study entry. All participants will be enrolled in A5350 where they will be randomized to either Arm A (Visbiome Extra Strength + stable ART; treatment arm) or Arm B (placebo for Visbiome Extra Strength + stable ART; control arm). Participants will be on the substudy for a total of 26 weeks. Probiotic therapy will be administered from week 2 to week 26. Colonic biopsies collected by flexible sigmoidoscopy will be obtained at entry and week 24 to assess tissue-specific effects related to immunologic outcomes, inflammation, bacterial translocation, and gut integrity. The lactulose/mannitol test will be administered at visits week 1 and week 26. The total sample size will be 40 participants (20 in Arm A, 20 in Arm B).

## 9.2 Outcome Measures

9.2.1 Primary Outcome Measure

Change from entry to week 24 in CD4+ T-cell count/area by IHC from colonic tissue biopsies.

- 9.2.2 Secondary Outcome Measures
  - 9.2.2.1 Change from entry to week 24 in CD8+ T-cell count/area by IHC from colonic tissues biopsies.
  - 9.2.2.2 Change from entry to week 24 in neutrophil infiltration quantified by myeloperoxidase staining/area in colonic mucosa by IHC.
  - 9.2.2.3 Change from entry to week 24 in expression of cytokines IL17 by CD4+ T-cells/area by IHC.
  - 9.2.2.4 Change from entry to week 24 in microbial translocation by enumerating bacterial products (LPS and 16sRNA)/area within the lamina propria by IHC.
  - 9.2.2.5 Change from week 1 to week 26 in measures of gut permeability after administration of the probiotic with the Lactulose/Mannitol Test.
  - 9.2.2.6 Change from entry to week 24 in microbial diversity via 16s rRNA sequencing from the colonic mucosal samples after Visbiome Extra Strength administration.
  - 9.2.2.7 Change from entry to week 24 in mucosal microbial metabolism of phophatidylcholide as measured by TMA and TMAO.

## 9.2.3 Exploratory Outcome Measure

Change from entry to week 26 in mucosal microbial metabolism by metabolomics and transcriptional analysis.

### 9.3 Randomization and Stratification

Treatment regimens will be assigned in A5350.

20.1	13.4	12*2=24	15*2=30
	16.4	16*2=32	20*2=40
5	19.4	22*2=44	28*2=56
22.1	13.4	10*2=20	13*2=26
	16.4	14*2=28	18*2=36
	19.4	19*2=38	24*2=48

The effect size of 20.1% is thought to be clinically meaningful based on available data. Compared to HIV negative subjects (56.4%), Mehandru et al [7] found decreased CD4+ frequency for HIV-infected naïve (19.3%), HIV-infected 1 year of ART (27.8%), and HIV-infected 3-7 years of ART (42.3%) populations [7]. In the SIV-macaques study, Klatt et al [56] found that the probiotic/prebiotic + ARV group had 46.13% CD4+ T-cells in the colon compared to 26.12% in the ARV alone group.

For each continuous secondary endpoint, change from entry to week 24 (and change from week 1 to week 26 for measures of gut permeability) will be compared between study arms. The following table summarizes the power to detect various effect sizes as well as the precision of the effect size estimate.

Comparison of 2 arms (16 vs. 16 evaluable participants)			
Effect size	Power	Width of 95% CI	
1.18*SD	90%	± 0.72*SD	
1.02*SD	80%	± 0.72*SD	
0.91*SD	70%	± 0.72*SD	

NOTE: If enrollment into the substudy is slow and proves to be prohibitive, we will alter the enrollment plan to a lower number of participants and perform analyses that are exploratory in nature.

## 9.5 Monitoring

Accrual, a summary of AEs related to biopsy, and sample/data availability will be reviewed monthly by the protocol core team. This summary will be pooled over the substudy arms. In addition, baseline characteristics as well as early substudy discontinuations (and reasons) will be reviewed regularly by the protocol core team.

An ACTG-appointed Study Monitoring Committee (SMC) will review accrual, biopsyrelated adverse event summaries, and off-study rates and reasons, and sample/data

availability, broken down by study arm. The first SMC review will occur 6 months after the first participant is enrolled and then every 6 months as long as participants remain in follow-up. Note that evaluation of biopsies for outcome measures will occur after follow-up is concluded, and, therefore these data are not expected to be available at interim reviews. The SMC may also be convened if a reason is identified by the DAIDS clinical representative, study chairs, or study statistician in consultation with the team.

## 9.6 Analyses

All statistical tests will be two-sided with a nominal alpha level of 0.05. Because this is a phase II substudy and all potential biologic activities of the intervention are of interest, analyses will be as-treated, and limited to participants who 1) have entry and week 24 biopsies, 2) remain on study product and ART through week 24 (participants with more than 50% on average of missed study product may be excluded), 3) have not used prohibited medications, 4) do not have a confirmed virologic failure (as defined per A5350 section 6.2.3) at or prior to week 24, and 5) do not experience inflammatory conditions, receive vaccines, or have concurrent illness (as defined per A5350 section 6.3.7).

NOTE: Participants experiencing inflammatory conditions at the time of a visit are instructed to wait 7 days before measurements are obtained. Measurements obtained while inflammatory conditions are present will not be included in the analysis.

A supplemental intent-to-treat analysis will also be performed and will include all enrolled participants. No adjustment for multiple testing will be performed.

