#### 6.2.3 Post-Entry Evaluations

#### **Pre-Treatment Evaluations**

Participants must begin treatment within 72 hours after the week 2 visit.

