4.3 Analysis Visit Windows

For all analyses, the following visit windows will be used:

- Screening: evaluations completed within 45 days of randomization.
- Entry (week 0): entry evaluations must occur on/after randomization and at least 24 hours after screening.
- Week 2: pre-treatment evaluation scheduled within a week [1, 3] window but prior to treatment initiation, treatment must begin within the next 72 hours after evaluation.
- On-treatment evaluations:
 - Week 4: weeks (3, 5]
 - Week 6: weeks (5, 8]
 - Week 14: weeks [12, 16]
 - Week 25 & 26: weeks [23, 28]
- Week 38: post-treatment evaluation scheduled within a week [36, 40] window.

If multiple results are available within the Week 6 or 14 visit windows the result closest to the scheduled visit will be used. If multiple results are available within the Week 38 window the result closest to 12 weeks after the last dose of study treatment (corresponding to protocol-defined 12 week washout) will be used.

Results within the weeks [23, 28] visit window will use the following logic to determine Week 25 and Week 26 results:

- If two results are collected on treatment the earlier will be Week 25 and the latter Week 26.
- If two results are collected off treatment the earlier will be Week 25 and the latter Week 26.
- If one result is collected on treatment and one result is collected off treatment the on treatment will be Week 25 and the off treatment Week 26.
- If only one result is collected it will be Week 25.
- If three or more results are available priority will be given to those collected on treatment and assigned Weeks based on the above rules.

For markers run in duplicate at entry and Week 2 and also at Weeks 25 and 26, "baseline" will refer to the average of entry and Week 2 and "Week 25/26" will refer to the average of Week 25 and Week 26. If only one result is available at either of these time points the single result will be used. For per-protocol analyses the "Week 25/26" calculation will only use results collected while on treatment.

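### The A5352s as-treated criteria end at week 24 although gut permeability is measured at week 26; in addition, the window for its pre-treatment test overlaps the earliest product start

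*Protocol*

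**What the plan says.** **Outcome.** A5352s 9.2.2.5 defines the permeability outcome as "Change from week 1 to week 26 in measures of gut permeability after administration of the probiotic with the Lactulose/Mannitol Test". The other substudy outcomes in 9.2.1 and 9.2.2 run from entry to week 24. A5352s 9.4 recognises the different dates for permeability.

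**Analysis set.** A5352s 9.6 gives a single as-treated definition. Criterion 1 is that participants "1) have entry and week 24 biopsies". Criterion 2 is "2) remain on study product and ART through week 24 (participants with more than 50% on average of missed study product may be excluded". Criterion 4 excludes confirmed virologic failure at or before week 24. Section 9.6.2 names the Wilcoxon rank-sum test for the other outcomes and adds no separate eligibility rule.

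**Parent study.** In A5350 9.6 the matching product and virologic-failure criteria run to week 26, as does the sCD14 endpoint. SAP 4.3 limits per-protocol week 25/26 values to those collected on treatment. SAP 4.4 counts a specimen taken 1 day after the last dose as on treatment. By its introduction, the SAP covers A5350 only.

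**Baseline timing.** The A5352s schedule puts the first test at week 1 ±4 days, under the heading "6.2.1 Screening and Pre-Treatment Evaluations". Section 6.2.1 says "Week 1 evaluations must be completed at least 4 days after entry evaluations unless otherwise specified". Section 6.3.3 says "Gut permeability assessment will be performed at least 7 days after flexible sigmoidoscopy". The A5350 schedule puts the week 2 visit at ±7 days, and A5350 6.2.3 says "Participants must begin treatment within 72 hours after the week 2 visit". For that parent visit, SAP 4.3 states the order expressly: "Week 2: pre-treatment evaluation scheduled within a week [1, 3] window but prior to treatment initiation". The documents contain no equivalent sentence for the substudy's week 1 test.

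**The concern.** An as-treated analysis is meant to describe people who were on product when the outcome was measured. For permeability the criteria stop about two weeks before the measurement. Product is planned through week 26 (A5352s 3.0), and participants who stop early stay in follow-up (A5350 6.2.4). Someone can therefore satisfy every criterion, stop after week 24, and contribute an off-product value as treated. The parent protocol avoids this by running its criteria to its endpoint.

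At the other end, the change score assumes a pre-product baseline. The heading says so, but the windows allow a test after the first dose, and no analysis rule would remove it.

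With 16 evaluable participants per arm, the comparison has 90% power only for an effect of 1.18 SD, so there is little room for dilution if it occurs.

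**Working it through.** **The plan's own figure.** Inputs from A5352s 9.4 and 9.6: 16 per arm, two-sided alpha 0.05. A two-sample t-test (noncentral t) gives power 0.898 for 1.18 SD, 0.797 for 1.02 SD and 0.702 for 0.91 SD, against the stated 90%, 80% and 70%. The CI half-width is t(0.975, 30) × √(2/16) = 2.042 × 0.354 = 0.72 SD, as stated. The table is reproduced.

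**Follow-up end (entry = day 0).**
- Week 24 = 24 × 7 = day 168. Week 26 = day 182, and ±7 days gives days 175 to 189.
- Stop on day 168: 175 − 168 = 7, 182 − 168 = 14, 189 − 168 = 21 days off product at the test.
- If week 24 is read as the actual biopsy visit, its earliest date is 168 − 7 = day 161, and the gap can reach 189 − 161 = 28 days. The schedule also puts the biopsy at least 14 days before week 26, so a 7-day gap arises only when the biopsy preceded the stop date.
- With the criteria carried to planned completion at day 182, the longest interval for someone who just qualifies is 189 − 182 = 7 days.

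**Baseline end (assuming parent and substudy entry fall on the same day).**
- Week 1 test: days 3 to 11 by the schedule (7 ± 4); 4 to 11 with the 4-day minimum in 6.2.1; 7 to 11 with the 7-day minimum in 6.3.3 if the biopsy is on day 0.
- Week 2 visit: 14 ± 7 = days 7 to 21. Product start up to 3 days later: days 7 to 24.
- Overlap under all three readings: days 7 to 11. Most product before the test: 11 − 7 = 4 days.
- Nominal dates: test on day 7, product from day 14, so no overlap.

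**What dilution could cost.** The documents give neither the share of Arm A stopping between week 24 and the test (f) nor the share of effect they would keep (r). Both are assumed here. Diluted effect = 1.18 × (1 − f(1 − r)), with power from the same t-test:

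| f | r = 0: effect, power | r = 0.5: effect, power |
|---|---|---|
| 5% | 1.12 SD, 0.87 | 1.15 SD, 0.88 |
| 10% | 1.06 SD, 0.83 | 1.12 SD, 0.87 |
| 20% | 0.94 SD, 0.73 | 1.06 SD, 0.83 |

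A rough check on f: suppose the whole ~20% missing-endpoint allowance in A5352s 9.4 were product discontinuation spread evenly over 24 weeks. The last two weeks would then hold 20 × 0.20 × 2/24 ≈ 0.3 participants per arm, about 2% of 16 and below the smallest row of the table.

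**The case against.** The strongest reply is that the protocol already expresses the intended exposure. Week 1 sits under a pre-treatment heading, the week 26 test sits under on-treatment evaluations, and product is planned from week 2 through week 26. A reader might infer from the windows and criteria that neither end of the outcome is tied to product. These headings contradict that. What is missing is a rule that enforces them.

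A reader might also infer that the estimate is biased toward zero. That would need an effect within days of starting one sachet daily, or loss of effect within one to three weeks of stopping. The documents show neither for permeability. A5350 1.2.8 and 1.3.5 hypothesise the reverse for related measures: persistence of microbiome changes, and of inflammation and translocation improvements for 12 weeks. This part of the objection stands.

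A third tempting reading is a 7-day baseline overlap, obtained by adding the 3-day fasting reschedule in Clarification Memo 1 to day 11. The memo does not say that a reschedule extends the ±4 day window, so only the 4-day figure is supported. Even that requires the week 2 visit to come before the week 1 test.

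It is also fair that few participants are likely to stop in the last two weeks, that a supplemental intent-to-treat analysis is planned, and that one analysis set built around the biopsies is a coherent choice. Test details are deferred to the MOPS, which is not available here and may fix the order of test and first dose. None of this removes the mismatch in 9.6: the written criteria end before this outcome is measured, and the SAP's on-treatment rules do not extend to the substudy.

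**Conclusion.** The point holds. For permeability, A5352s criteria 2 and 4 end at week 24 and the measurement is at week 26. A participant nominally 14 days off product (7 to 21, taking week 24 as day 168) is analysed as treated, contrary to the standard the parent study applies to its own endpoint.

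The baseline issue is real but smaller: at most 4 days of product, none at nominal dates, assuming same-day parent and substudy entry. The documents do not state that assumption, and a later substudy entry would widen the overlap.

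Any effect on the estimate is possible dilution whose size cannot be derived from the documents. The planned 16 per arm and the stated power do not change. The finding concerns one secondary outcome; the primary biopsy outcome, entry to week 24, matches its criteria.

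**What to change.** 1. In A5352s 9.6, add: *For 9.2.2.5, criteria 2 and 4 apply through the week 26 lactulose/mannitol test or planned completion of study product at week 26, whichever is earlier.* The second limb matters. Without it, completers tested up to 7 days after planned completion would be dropped.
2. Consider adopting the SAP 4.4 on-treatment convention (specimen within 1 day of last dose) for participants who stop early.
3. State in A5352s 9.6 that the baseline permeability value used in the analysis must have been collected before the first dose.
4. Reconcile the timing statements with the pre-treatment heading: the week 1 window in A5352s 6.1, the 4-day minimum in 6.2.1, the 7-day minimum in 6.3.3, and the week 2 window in A5350 6.1. Which of them should govern is for the study team to settle.

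The cost is two sentences plus the reconciliation. A few late stoppers or post-dose baselines would leave the as-treated set for this one outcome, a further post-randomisation exclusion in a small sample. The intent-to-treat analysis of all enrolled participants remains as the check on it.
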